3.2 STUDY DESIGN

This is a randomized, double-blinded, placebo-controlled, single-center study intended to investigate very low dose systemic (IV) tPA along with standard anticoagulation therapy followed by standard dose oral apixaban as a treatment for intermediate-high risk (submassive) PE. To date, studies have demonstrated that full dose (100 mg) and half-dose (50mg) systemic (IV) tPA are effective for lysing clot; however, at the expense of clinically significant bleeding. Catheter-directed trials have shown that 24mg of tPA can be administered through a pulmonary artery catheter with clinical improvement in obstructive index and RV/LV ratio without an increased risk of bleeding. However, such procedures are time consuming, expensive, and there is the concern for clinical decompensation during the intervention. To date, no study has tested whether the same low dose (24mg) of systemic (IV) tPA could be delivered systemically with equally favorable results.

In this trial, 40 patients (20 per arm) will be randomly assigned using a computer program at Cedars-Sinai Medical Center in Los Angeles, California. Additional subjects may be consented to compensate for screening failures and/or treated patients who lack sufficient data. The study is planned to evaluate the reduction in clot burden (obstruction index using the Refined Modified Miller Score), improvement in RV dysfunction, and overall safety in the two treatment groups. Subjects with intermediate-high risk PE (hemodynamically stable PE with a RV dysfunction and an, elevation in Troponin and/or BNP) will be randomized to one of two treatment groups: 24mg of systemic (IV) tPA + IV unfractionated heparin followed by the oral anticoagulant, apixaban, versus saline placebo + IV unfractionated heparin followed by oral apixaban.

Apixaban was chosen as the anticoagulant of choice due to its favorable bleeding profile in initial studies, which is an important consideration when using an anticoagulant following systemic thrombolysis.

Bleeding, recurrent PE and serious adverse events will be collected and reported throughout the study. Specific reporting for the primary safety (major bleeding) events will occur during the first 72 hours. We will continue monitoring for bleeding (secondary safety endpoints) for up to 30 days.

All imaging studies will be sent to the Syntactx core imaging laboratory for evaluation. Procedures for transfer of images from study site to Syntactx will be provided and we will maintain patient HIPAA confidentiality. Results of the assessments will be blinded and entered into the clinical database. All data from the study will be blinded and exclude information regarding the drug administered. Subjects will return for follow-up clinic evaluations at Day 30, 180 and 365 ± 15 days. It is anticipated that the clinical study duration will be up to 24 months including first subject enrolled through to last subject completed or until the study is formally terminated. An individual subject's participation will be approximately 1 year.

The figure below shows the schematic summary of the trial design:

* Provided bleeding risk is deemed acceptable, patients will be immediately started on apixaban 24 hours after study drug administration. The duration of total anticoagulation will be determined by the treating physician based on clinic judgement, risk of recurrence, and whether the initial PE was provoked.

3.3. STUDY POPULATION

3.3.1. INCLUSION CRITERIA

Patients eligible for the trial must comply with the following at randomization:

- Male or female 18-75 years in age
- Chest CT angiogram evidence of proximal PE with a filling defect in at least one main pulmonary artery or lobar artery
- PE symptom duration ≤14 days

- Intermediate-high risk PE: defined as PE with significant clot burden, RV dysfunction elevation in either troponin and/or BNP. and hemodynamically stable (systolic blood pressure>90mm Hg without the use of vasopressor support)
- Randomization within 36 hours of anticoagulation
- Signed and dated informed consent obtained from subject or Legally Authorized Representative before initation of any study procedures

3.3.2. EXCLUSION CRITERIA

Patients with any one of the following will be excluded from participation in this clinical trial:

- Stroke or transient ischemic attack (TIA), head trauma, or other active intracranial or intraspinal disease within one year
- Recent (within one month) or active bleeding from a major organ
- Major surgery within seven days
- Clinician deems the subject too high-risk for bleeding using HAS-BLED criteria
- History of any hematologic disease or coagulopathy
- Cirrhosis (as determined by Child-Pugh B or C)
- History of heparin-induced thrombocytopenia (HIT)
- Hemodynamic instability defined as systolic blood pressure (SBP) less than 90 mm Hg and/or use of vasopressors for greater than 15 minutes
- Severe hypertension as define as systolic blood pressure (SBP) greater than 180 mm Hg
- Cardiac arrest or active cardiopulmonary resuscitation (CPR)
- Receiving neuraxial anesthesia or undergoing spinal puncture
- Patient with prosthetic heart valves
- Evidence of irreversible neurological compromise
- Evidence of poor functional status
- History of a major gastrointestinal bleed
- Active gastric or duodenal ulcers
- Use of thrombolytics or glycoprotein IIb/IIIa antagonists within 3 days prior to diagnosis
- Lovenox administration within 12 hours of randomization
- Direct-acting oral anticoagulant use (dabigatran, rivaroxaban, apixaban, or edoxaban) with last known dose within 48 hours.
- Hemoglobin < 10 g/dL
- platelets < 100 thousand/µL
- INR > 1.4
- Alanine transaminase (ALT) or aspartate transaminase (AST) \geq 2 times upper limit of normal (ULN)
- Total bilirubin (TBL) \geq 1.5 times ULN (except due to confirmed Gilbert's syndrome)
- creatinine clearance < 30 mL/min
- Patient is pregnant (positive pregnancy test; women of childbearing capacity must be tested prior to enrollment) or breast feeding
- Patient who is a prisoner, or if subject who becomes compulsory detained
- Active cancer defined as diagnosis of cancer within six months before the study inclusion, or receiving treatment for cancer at the time of inclusion or any treatment for cancer during 6 months prior to randomization, or recurrent locally advanced or metastatic cancer
- Known allergy, hypersensitivity or thrombocytopenia from heparin, tPA, apixaban, or iodinated contrast except for mild-moderate contrast allergies for which steroid pre-medication can be be administered within 12 hours prior to the CTA.
- HIV/AIDS

• Weight>130 kg or < 40 kg.on day of randomization

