Inclusion Criteria	 Male or female 18-75 years in age Chest CT angiogram evidence of proximal PE with a filling defect in at least one main pulmonary artery or lobar artery PE symptom duration ≤14 days Intermediate-high risk PE: significant clot buden with RV dysfunction, an elevation in troponin > 0.05 ng/mL and/or brain natriuretic peptide (BNP) > 100 pg/mL, and hemodynamically stable (systolic blood pessure>90mm Hg without the use of vasopressor support) Randomization within 36 hours of anticoagulation Signed and dated informed consent obtained from subject or legally authorized representative before initiation of any study procedures
Exclusion Criteria	 Stroke or transient ischemic attack (TIA), head trauma, or other active intracranial or intraspinal disease within one year Recent (within one month) or active bleeding from a major organ Major surgery within 14 days Clinician deems the subject too high-risk for bleeding using HAS-BLED criteria. History of any hematologic disease or coagulopathy Cirrhosis (as determined by Child-Pugh B or C) History of heparin-induced thrombocytopenia (HIT) Hemodynamic instability defined as systolic blood pressure (SBP) less than 90 mm Hg and/or use of vasopressors for greater than 15 minutes Severe hypertension as define as systolic blood pressure (SBP) greater than 180 mm Hg Cardiac arrest or active cardiopulmonary resuscitation (CPR) Receiving neuraxial anesthesia or undergoing spinal puncture

Γ

	 Patient with prosthetic heart valves Evidence of irreversible neurological compromise Evidence of poor functional status History of major gastrointestinal bleed within the last month Active gastric or duodenal ulcers Use of thrombolytics or glycoprotein IIb/IIIa antagonists within 3 days prior to diagnosis Lovenox administration within 12 hours of randomization Direct-acting oral anticoagulant use (dabigatran, rivaroxaban, apixaban, or edoxaban) with last known dose within 48 hours Hemoglobin < 10 g/dL

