5.3. RANDOMIZATION TO TREATMENT

A subject who has signed informed consent and meets all eligibility criteria will be randomized by computer to receive either very low dose systemic (IV) tPA (24mg) + anticoagulation vs normal saline placebo (of same volume as systemic [IV] tPA) + anticoagulation. Subjects will be transitioned to apixaban 24 hours after study drug administration if subjects have no evidence of active bleeding nor significant hemoglobin drop (i.e. $\geq 2 \text{ mg/dL}$).

All patients who give consent for participation and who fulfill the inclusion/exclusion criteria will be randomized. Randomization will be requested by the staff member responsible for recruitment from Randomize.net.

In return, Randomize.net will send an answer form to the research pharmacy, who are not involved in assessing outcome of the study. This form will include a randomization number. A closed envelope with printed randomization numbers on it are available on-site. For every randomization number, the corresponding code for the therapy group of the randomization list will be found inside the envelopes. The research pharmacy will open the envelope and will find the treatment condition to be conducted. Treatment medication will be prepped according to the randomization assignment. Staff responsible for recruitment and symptom ratings is not allowed to receive information about the group allocation.

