5.4. STUDY INTERVENTIONS

Eligible patients will be randomized in equal proportions between very low dose systemic (IV) tPA (24mg) + IV unfractionated heparin or saline placebo + IV unfractionated heparin. Study drug will be infused as follows: 4mg bolus IV push over 1 minute followed by 20mg infused IV over 19 minutes.

The study drug will be purchased from Genentech in its commercially available recombinant form. The study drug and placebo will be relabelled by the Cedars-Sinai Medical Center Research Pharmacy according to MHRA (Medicines and Healthcare Regulatory Agency) guidelines.

Study drug will be administered within 36 hours of anticoagulant administration. Study drug or placebo will be administered to the patient by a study-trained nurse while the patient is in hospital. All personnel will be blinded to the identity of the IV bag contents.

SAFE-LYSE Flowchart of Procedures											
Procedures	Baseline up to 48 hours pre study medication	Day 0	Day 1	Day 2	Day 3 & Day 7	Day 30 + 15 days (Clinic Visit)	Day 90 + 15 days (Phone contact)	Day 180 + 15 days (Clinic contact)	Day 270 + 15 days (Phone contact)	Day 365 + 15 days (Clinic Visit)	ET1
Informed consent	x										
Inclusion/Exclusion	x										
Randomization		x									
Heparin anticoagulation therapy ²	x	x	x								
Pregnancy test (if applicable)	x										
Medical and demographic history	x										
Physical exam	x		x			x		x		x	x
Vital signs including pulse ox	x	x	x	x		x		x		x	x

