Twenty-four hours after study drug administration, when the bleeding risk is determined to be low by the treating physician (i.e. no active bleeding nor significant hemoglobin drop $\geq 2 \text{ mg/dL}$), post-intervention evaluations are complete, the patient is tolerating oral medications, and the patient's creatinine clearance is >30 mL/min, the IV unfractionated heparin will be stopped. Provided bleeding risk is deemed acceptable, they will be immediately started on apixaban (Eliquis) 10 mg twice-daily x one week followed by 5 mg twice-daily for at least 6 months. Based on patient-specific factors, including unprovoked nature of PE event, and/or persisting DVT/PE risk factors, consideration will be given for decreasing the apixaban dose to 2.5 mg twice-daily after 6 months for the remainder of the study. The duration of total anticoagulation will be determined by the treating physician based on Clinic judgement, risk of recurrence, and whether the initial PE was provoked. Apixaban will be dispensed on Day 1, 30, and 180.

Timing of Thrombolytic Intervention

The subject will receive 24 mg of systemic (IV) tPA vs normal saline placebo within 24 hours of initiaition of anticoagulation therapy.

Systemic (IV) tPA

Commercially available formulation of systemic (IV) tPA (Genentech) may be used and all instructions for reconstitution provided in the package insert should be followed. tPA will be specially labeled for the study. The systemic (IV) tPA will be infused as follows: 4mg bolus followed by infusion at a rate of 20mg over 19 minutes for a total of 24mg.

Normal Saline Placebo

The pharmacy will prepare a normal saline placebo packaged in the same fashion as the systemic (IV) tPA. The saline will be infused as follows: 4mg bolus followed by infusion at a rate of 20mg over 19 minutes for a total of 24mg.

Day 0 Assessments: Pre-Infusion and Post-Infusion

- Vital signs including temperature, respiratory rate, heart rate, blood pressure, and oximetry will be obtained.
- Assessment of adverse events and bleeding events.

Day 1 Assessments

- Vital signs including temperature, respiratory rate, heart rate, blood pressure, and oximetry will be obtained.
- Physical Examination will be completed.

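### The synopsis and body give different limits for recent major surgery, past major GI bleeding and time to dosing, and nothing says which governs

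*Combined protocol and SAP*

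**What the plan says.** **Major surgery.** The synopsis exclusion list has "Major surgery within 14 days". Section 3.3.2 has "Major surgery within seven days".

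**Major gastrointestinal bleeding.** The synopsis has "History of major gastrointestinal bleed within the last month". Section 3.3.2 has "History of a major gastrointestinal bleed", with no time limit. Both lists also carry a separate exclusion for active bleeding, or bleeding in the past month, from a major organ.

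**Time from anticoagulation.** The synopsis and Section 3.3.1 both require "Randomization within 36 hours of anticoagulation". Section 5.4 says "Study drug will be administered within 36 hours of anticoagulant administration". Section 5.4.1, under the timing of the thrombolytic, says the subject receives tPA "vs normal saline placebo within 24 hours of initiaition of anticoagulation therapy".

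**What ties these together.** Section 5.3 says "All patients who give consent for participation and who fulfill the inclusion/exclusion criteria will be randomized", and has the pharmacy prepare the drug after assignment. Section 9.1.1 says the study follows the approved protocol. It does not rank the synopsis against the body, or one section against another.

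**The concern.** The first two items are bleeding-related exclusions applied before a thrombolytic. Major bleeding within 72 hours is the primary safety endpoint (Section 1.2.3). The stopping rules in Section 3.5 act on very small counts: one fatal intracranial haemorrhage, two of any kind, or three severe bleeds. With about 20 patients per arm, a bleed in one patient whose eligibility is disputed would be awkward to interpret. Section 6.3.2 relies on careful screening to ensure that every enrolled patient meets all criteria, and that cannot be done consistently while two lists disagree.

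The third item concerns compliance, not a demonstrated bleeding risk. A dose given at 30 hours satisfies one sentence of the protocol and breaks another. Section 9.1.1 bars deviations without IRB approval except for immediate danger, and Section 2.2 sends deviations to the IRB and the funder. Staff therefore cannot tell whether such a dose has to be reported.

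**Working it through.** There is no power or error-rate figure to reproduce. The check sets the current texts side by side.

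| Item | One place | Another place | Group in conflict |
|---|---|---|---|
| Major surgery | Synopsis: 14 days | 3.3.2: 7 days | Days 8 to 14 |
| Major GI bleed | Synopsis: last month | 3.3.2: any history | Bleeds more than one month old |
| Dosing limit | 5.4: 36 h | 5.4.1: 24 h | 24 to 36 h |

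**Surgery.** The gap is 14 − 7 = 7 days. A patient at day 10 is excluded by the synopsis and is not excluded by this criterion in Section 3.3.2. The full eligibility section is the looser one.

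**GI bleed.** Section 3.3.2 cannot be read as silently meaning one month, because the same list already has its own one-month exclusion for major-organ bleeding. Bleeds within the month are excluded under both lists, so only older bleeds are in dispute. Here the synopsis is the looser one.

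**Choosing one list does not help.** The synopsis is stricter on surgery and Section 3.3.2 is stricter on GI bleeding. Following either list throughout gives the more cautious rule on one item only. Applying the stricter rule item by item would satisfy both lists, but the protocol does not say to do so.

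**Dosing.** The gap is 36 − 24 = 12 hours, and 12/36 = 33% of the randomisation window. Take a patient who consents, meets every criterion and is randomised at 30 hours:

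1. The synopsis and Section 3.3.1 permit this, and Section 5.3 says such a patient will be randomised.
2. Section 5.4 permits dosing up to 36 hours.
3. Section 5.4.1 required dosing by 24 hours, which has already passed.

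Dosing everyone by 24 hours would satisfy both dosing sentences, but not for a patient randomised after 24 hours. For that group no cautious reading resolves the conflict.

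**Weight of one patient.** The documents do not give the distribution of time since surgery, time since bleed or time to randomisation, so the number affected is unknown. One patient is 1/20 = 5% of an arm, or 1/40 = 2.5% of the trial.

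**Effect on the outcome window.** The follow-up CTA is timed from the end of study treatment (Section 5.4.1, Day 1). A patient is evaluable on having valid CTAs and a completed infusion (synopsis, Sample Size). Whether the dosing limit is 24 or 36 hours therefore does not shift the outcome window.

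**The case against.** The strongest reply is that this is editorial tidying. Eligibility is settled before randomisation, so no bias between arms follows. The clinician's HAS-BLED exclusion, the undue-hazard clause in Section 3.5, stopping the infusion if bleeding occurs (Section 6.3.2) and the stopping rules all limit exposure. On GI bleeding the full eligibility section is already the stricter text. Only the surgery item leaves the body looser on a bleeding criterion. All of that is correct, and it limits how serious the point is. Those safeguards nevertheless leave the rule to individual judgement, and none of them reconciles the two dosing limits.

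Three narrower objections deserve an answer.

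- The 36-hour figure appears in three places and 24 hours in one, but two of the three are randomisation limits. On dosing itself the count is one against one. This stands, so the case for 36 hours rests on its fit with the randomisation window, not on a majority.
- The clocks are worded differently: Section 5.4 refers to anticoagulant administration, and Section 5.4.1 to its initiation. The natural reading is that both mean the start of anticoagulation, and the 12-hour gap assumes this.
- The 33% is a share of permitted hours and the 5% applies to any single patient. Neither estimates how many patients are affected. This also stands.

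It can further be argued that dosing at 24 to 36 hours is no deviation, since Section 5.4 expressly allows it. That is a fair reading, but Section 5.4.1 supports the opposite one equally well.

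**Conclusion.** The concern holds. All three conflicts are in current text. Items 1 and 2 make the same patient eligible under one list and excluded under the other. Item 3 cannot be complied with for patients randomised 24 to 36 hours after starting anticoagulation. The surgery item carries most weight, because there the body text is looser than the synopsis on a bleeding-related criterion.

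The consequence is limited: no effect on the treatment estimate, the power or the CTA window is shown. The conclusion assumes that the anticoagulation clock starts at the same moment in every section. The absence of a precedence rule is confirmed only for the text available, from which some pages had been removed. This should be corrected, but it does not threaten the trial's main comparison.

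**What to change.** Put one rule in every place:

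- **Surgery:** change Section 3.3.2 to 14 days.
- **Major GI bleed:** change the synopsis to any history.
- **Dosing:** change 24 to 36 hours in Section 5.4.1, to agree with Section 5.4 and fit the randomisation window. Use one wording for the start of the clock throughout. Because drug is prepared only after randomisation, state that the dosing limit is the binding one.

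The two stricter exclusions satisfy both current lists. Nothing in the documents shows which version was intended, so if the investigators prefer a looser rule they should justify it and state it in both places. If 24 hours is what they want, the randomisation window in the synopsis and Section 3.3.1, and the limit in Section 5.4, must be shortened to fit.

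The cost is one short amendment and a revised eligibility checklist. The stricter exclusions narrow the eligible pool slightly, and choosing 24 hours would narrow it further. The analysis and planned sample size do not change.

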3.3.3 WOMEN OF CHILDBEARING POTENTIAL

Women of childbearing potential is defined as any female who has experienced menarche and who has not been surgically sterilized or is not postmenopausal. Menopause is as 12 months of amenorrhea in a woman over age 45 in the absence of other physiological causes. Serum beta human chorionic gonadotropin (β -hCG) pregnancy test will be performed at the Screening Visit on all women of childbearing potential.

During the duration of the study, women of childbearing potential must agree to use two effective birth control methods (for example: birth control pills, condoms, etc) at the same time, and be able to comply with effective contraception without interruption during the study therapy (including dose interruptions).

3.4. CONCOMITANT TREATMENTS

3.4.1 PROHIBITED AND/OR RESTRICTED TREATMENTS

The following systemic medications may increase the risk of bleeding and will not be concurrently administered during the study:

- Other antithrombotic agents such as vitamin K antagonists (i.e., warfarin)
- Other factor Xa inhibitor oral anticoagulants (e.g. rivaroxaban, edoxaban, or betrixaban)
- Fondaparinux or low molecular weight heparins
- direct thrombin inhibitors (dabigatran, argatroban, bivalirudin, lepirudin, etc.)
- glycoprotein IIb/IIIa antagonists during the thrombolytic infusion
- NSAIDS

3.4.2 OTHER RESTRICTIONS AND PRECAUTIONS

None

3.5. DISCONTINUATION OF SUBJECTS FROM TREATMENT

Discontinuation of alteplase

If a subject develops the following adverse events the alteplase infusion will be permanently discontinued:

- SAE or other safety concern that is related to study drug treatment
- New onset of neurological symptoms
- New onset of severe headache
- Major life-threatening bleeding (per GUSTO criteria)
- Initiating or continuing study drug places the subject at undue hazard as determined by the Investigator

The subject will continue to be followed for the remainder of the study. The subject will be assessed immediately after the infusion and appropriate clinical treatment will be instituted.

One of the PIs will use his clinical judgment to determine the treatment needed and this may include imaging studies, blood transfusions and IVC filter placement. Once the subject is stabilized, if anticoagulant therapy is considered a clinical option, the subject will be started on apixaban per protocol.

Discontinuation of Apixaban

If a subject must be discontinued from apixaban before the end of the study, this will not result in automatic withdrawal of the subject from the study, and the subject should continue to be followed for efficacy and safety outcomes.

A subject should be discontinued from apixaban if:

- The investigator believes that for safety reasons (ie, adverse event) it is in the best interest of the subject to stop apixaban.
- The subject develops any condition which requires anticoagulation or thromboprophylaxis (ie, atrial fibrillation, VTE).
- The subject becomes pregnant.
- The subject requests to discontinue apixaban permanently
- The subject has a major life-threatening bleed (per GUSTO criteria);

If the subject permanently discontinues apixaban before the 6-month visit, he/she should be instructed to complete an unscheduled visit and the remaining scheduled visits. The investigator will provide a narrative to describe any adverse events that occur up to apixaban discontinuation. The appropriate adverse event or serious adverse event sections of the eCRF are to be completed.

A subject should have apixaban administration interrupted if the following conditions occur:

- Bleeding that is significant that does not fit GUSTO criteria
- Alanine transaminase (ALT) or aspartate transaminase (AST) ≥ 2 times upper limit of normal (ULN)
- Total bilirubin (TBL) ≥ 1.5 times ULN (except due to confirmed Gilbert's syndrome)
- Subjects with a significant drop in hemoglobin
- Consider discontinuation / follow if Hgb < 10

The PI will use clinical judgment to determine course of action (labs, imaging studies, etc.) and decide when and if the apixaban can be restarted.

Withdrawal from the Study

A subject will be withdrawn from the study for any of the following reasons:

- Lost to follow-up (only after all means of all subsequent contact, including locator services where permitted by law) or,
- Withdrawal of consent (unless specifically refused by the subject. Subject contact will be made to obtain vital status and other outcomes at the 3, 6- and 12-month visit).

If a subject is lost to follow-up, every reasonable effort must be made by the study site personnel to contact the subject and determine the reason for discontinuation/withdrawal. The measures taken to follow up must be documented.

If a subject withdraws consent from study or is lost to follow-up, his or her vital status and other outcomes will be collected at the Day 30, 180 and 365 visits either by telephone or in person, or if applicable, by a review of the subject's medical or public records unless this contact is not allowed by local regulations.

Stopping rules at the interim analysis for the treatment (tPA) group would involve:

- Severe bleeding in the first 72 hours:
 - -One fatal intracranial hemorrhage (ICH)
 - -Two ICH of any kind
 - -Severe or life-threatening bleed rate of 15%; i.e., three patients (GUSTO criteria)

- Two cases of death from acute PE (in either group), if occurring during hospitalization (deterioration in a patient who survives will not be considered in stopping rules).
- Any other issue that the DMC believes merits discontinuing the trial.

